11.4 Efficacy analysis and statistical methods

11.4.1 Analysis of the primary endpoint

Categorical variables will be statistically analyzed and described using counts (percentages). Without performing multivariate adjustment, the primary endpoints of the two groups will be compared in the ITT analysis set, PPA analysis set, and ATA analysis set respectively. The absolute risk differences and their 95% confidence intervals (95% CI) will be used to describe the differences between the two groups. In addition, in the PPA analysis set, the chi - square test or Fisher's exact test will be used to analyze the variables related to the primary endpoint. Multivariate logistic regression will be used to adjust for factors that may affect the primary endpoint and to analyze the independent risk factors influencing the primary endpoint. During this process, continuous variables will be converted into categorical variables. The variables used for adjustment include the patient grouping (bladder training/direct removal), tumor location (the lower border of the tumor is above the peritoneal reflection/the lower border of the tumor is below the peritoneal reflection), gender (male/female), and age (≤ 65 years/ > 65 years) in the PPA dataset. Besides the above - mentioned variables, variables with a p - value < 0.1 in the univariate analysis will also be included. The adjusted differences between groups will be described using odds ratios (OR) and 95% CI.

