6.4.1 Preoperative characteristics

- Sex, categorical variable: male, female;
- Age, continuous variable, measured in years;
- Body Mass Index, continuous variable, measured in kg/m²;
- American Society of Anesthesiologists grading, categorical variable: I, II, III, IV;
- Neoadjuvant radiotherapy/chemoradiotherapy, categorical variable: no, yes;
- Tumor site, categorical variable: the lower edge of the tumor is above the peritoneal reflection, the lower edge of the tumor is not above (below or at) the peritoneal reflection.
- The distance from the lower edge of the tumor to the anal margin, continuous variable, measured in centimeter;
- Benign prostatic hyperplasia, categorical variable: No, Yes;
- History of hypertension, categorical variable: No, Yes;
- History of diabetes, categorical variable: No, Yes;
- ICIQ-SF score at admission, continuous variable, measured in points;
- ICIQ-SF classification at admission, categorical variable: no or mild, moderate, severe;
- IPSS score at admission, continuous variable, measured in points;
- IPSS classification at admission, categorical variable: mild, moderate, severe;
- Clinical T stage, categorical variable: clinical complete response (cCR), T1, T2, T3, T4;
- Clinical N stage, categorical variable: N0, N1, N2;
- Clinical TNM stage, categorical variable: 0 stage, I stage, II stage, III stage, IV stage.

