6.4.2 Operative characteristics

- Surgical techniques, categorical variable: laparoscopic-assisted surgery, robotic-

assisted surgery;

- Surgical procedure, categorical variable: low anterior resection (LAR), abdominoperineal resection (APR). Subtypes of LAR include LAR with prophylactic enterostomy, LAR with intersphincteric resection (ISR), LAR with Turnbull-Cutait Pull-Through Coloanal Anastomosis (TCA), LAR with transanal total mesorectal excision (TaTME). There is overlap among different subtypes of LAR.
- Operation time, continuous variable, measured in minutes;
- Anastomosis, categorical variable: no anastomosis, colorectal anastomosis, coloanal anastomosis;
- Intraoperative blood loss volume, continuous variable, measured in milliliters;
- Intraoperative urine output volume, continuous variable, measured in milliliters;
- Intraoperative intravenous infusion volume, continuous variable, measured in milliliters;

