6.5 Analysis of endpoints

6.5.1 Analysis of the primary endpoint

Categorical variables will be statistically analyzed and described using counts (percentages). Without multivariate adjustment, the primary endpoints of the two groups will be compared respectively in the ITT analysis set, the PPA set, and the ATA set. The differences between the two groups will be described using the absolute risk differences (ARD) and their 95% Confidence Intervals (95% CI). The 95% CI will be compared with an absolute risk difference of 0.

The positive primary endpoint consists of bladder residual urine volume (RUV) $>100\text{ml}$ after the first voiding or secondary catheterization within 7 days after the catheter removal. These two subtypes will also be compared between the two groups and their 95% confidence interval will be presented. Also, secondary catheterization for reasons other than urinary retention will be listed in the subsets of secondary catheterization.

Primary endpoint:

Dataset: ITT, PPA and ATA				
Variables	Free-drainage group N=***	ICCAUT group N=***	Absolute risk difference (95% CI)	P value
Urinary dysfunction	** (**)	** (**)	** (** to **)	*.***
RUV >100ml	** (**)	** (**)	** (** to **)	-
Secondary catheterization	** (**)	** (**)	** (** to **)	-
Urinary retention	** (**)	** (**)	** (** to **)	-
Not urinary retention (notes on the specific reasons)	** (**)	** (**)	** (** to **)	-
Missing data	** (**)	** (**)		

In addition, in the PPA set, the Chi-square test or Fisher's exact test will be used to analyze the variables related to the primary endpoint. Multivariate logistic regression will be employed to adjust the factors that may have an impact on the primary endpoint, and to analyze the independent risk factors affecting the primary endpoint. During this process, continuous variables will be transformed into categorical variables. The variables used for adjustment include the patient grouping in the PPA dataset (ICCAUT group/free-drainage group), tumor site (the lower edge of the tumor is above the peritoneal reflection/the lower edge of the tumor is below the peritoneal reflection), sex (male/female), and age (≤ 65 years old/ > 65 years old). In addition to the above variables, variables with a p-value < 0.1 in the univariate analysis will also be included. After adjustment, the differences between the groups will be described using the Odds Ratio (OR) and 95% CI.

Univariate analysis:

Dataset: PPA	
17 Mar 2025	SAP version 1.0

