Variables	Without Urinary dysfunction N=***	With Urinary dysfunction N=***	P value
Interventions			*.***
Free drainage	**(**)	**(**)	
ICCAUT	**(**)	**(**)	
Sex			*.***
Male	**(**)	**(**)	
Female	**(**)	**(**)	
Age			*.***
≤ 65 years old	**(**)	**(**)	
> 65 years old	**(**)	**(**)	
BMI			*.***
<24 kg/m^2	**(**)	**(**)	
≥24 kg/m^2	**(**)	**(**)	
ASA			*.***
I-II	**(**)	**(**)	
III-IV	**(**)	**(**)	
Neoadjuvant radiotherapy or chemoradiotherapy			*.***
No	**(**)	**(**)	
Yes	**(**)	**(**)	
Tumor site			*.***
Above the peritoneal reflection	**(**)	**(**)	
Below or at the peritoneal reflection	**(**)	**(**)	
Distance from the anal verge to the tumor			*.***
≤5 cm	**(**)	**(**)	
>5 cm	**(**)	**(**)	
Benign prostatic hyperplasia			*.***
No	**(**)	**(**)	
Yes	**(**)	**(**)	
IPSS classification at admission			*.***
Mild	**(**)	**(**)	
Moderate	**(**)	**(**)	
Severe	**(**)	**(**)	
ICIQ-SF classification at admission			*.***
No or mild	**(**)	**(**)	
Moderate	**(**)	**(**)	

Severe	**(**)	**(**)	
History of hypertension			*.***
No	**(**)	**(**)	
Yes	**(**)	**(**)	
History of Diabetes			*.***
No	**(**)	**(**)	
Yes	**(**)	**(**)	
Pathological stage T			*.***
pCR to T2	**(**)	**(**)	
T3 to T4	**(**)	**(**)	
Pathological stage N			*.***
N0	**(**)	**(**)	
N1 to N2	**(**)	**(**)	
Pathological stage TNM			*.***
0 to II	**(**)	**(**)	
III to IV	**(**)	**(**)	
Surgical techniques			*.***
Laparoscopic-assisted surgery	**(**)	**(**)	
Robotic-assisted surgery	**(**)	**(**)	
Surgical procedure			*.***
LAR	**(**)	**(**)	
APR	**(**)	**(**)	
Operation time			*.***
≤180 minutes	**(**)	**(**)	
>180 minutes	**(**)	**(**)	
Anastomosis			*.***
No anastomosis	**(**)	**(**)	
Colorectal anastomosis	**(**)	**(**)	
Coloanal anastomosis	**(**)	**(**)	
Intraoperative urine output volume			*.***
≤500 ml	**(**)	**(**)	
>500 ml	**(**)	**(**)	
Intraoperative intravenous infusion volume			*.***
≤1500 ml	**(**)	**(**)	
>1500 ml	**(**)	**(**)	
Duration of the indwelling urethral catheter			*.***

≤2 days	**(**)	**(**)	
>2 days	**(**)	**(**)	
Urinary tract infections			*.***
No	**(**)	**(**)	
Yes	**(**)	**(**)	

Multivariate analysis:

Dataset: PPA				
Variables	Without Urinary dysfunction N=***	With Urinary dysfunction N=***	Adjusted OR (95% CI)	P value
Interventions				*.***
Free drainage	**(**)	**(**)		
ICCAUT	**(**)	**(**)	** (** to **)	
Sex				*.***
Male	**(**)	**(**)	** (** to **)	
Female	**(**)	**(**)		
Age				*.***
≤ 65 years old	**(**)	**(**)		
> 65 years old	**(**)	**(**)	** (** to **)	

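### Categorising every continuous covariate before the p<0.1 screen and the per-protocol logistic model costs power to find risk factors; the treatment comparison is hardly touched

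*SAP*

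**What the plan says.** SAP 6.4 defines the covariates as measured. Examples are "Age, continuous variable, measured in years" and "Operation time, continuous variable, measured in minutes". BMI, distance of the tumour from the anal margin, intraoperative urine output, infusion volume and the admission IPSS and ICIQ-SF scores are also listed as continuous. The two scores appear a second time as classes, for example "IPSS classification at admission, categorical variable: mild, moderate, severe".

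SAP 6.5.1 then sets the rule for the per-protocol univariate tests and the multivariable logistic model: "During this process, continuous variables will be transformed into categorical variables". Protocol v2.0 section 11.4.1 agrees: "During this process, continuous variables will be converted into categorical variables".

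- **Forced-in terms.** Besides treatment group and tumour site, the list has "sex (male/female), and age (≤ 65 years old/ > 65 years old".
- **Screened terms.** In addition, "variables with a p-value < 0.1 in the univariate analysis will also be included". The univariate test is chi-square or Fisher's exact.
- **Cut-points.** The univariate table shell cuts age at 65 years, BMI at 24 kg/m², "Distance from the anal verge to the tumor" at 5 cm, operation time at 180 minutes, urine output at 500 ml and infusion volume at 1500 ml. IPSS and ICIQ-SF each have three levels.
- **Onward use.** SAP 6.5.4 adds as subgroups any variables that the multivariable model finds independently associated with the endpoint.

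The primary comparison, by contrast, is an absolute risk difference without covariate adjustment.

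**The concern.** A cut treats patients just either side of it as different and everyone on one side as alike. If risk changes smoothly with age or operation time, part of what was measured is discarded before the analysis starts.

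The model has two stated purposes: adjustment, and identification of independent risk factors. The second is exposed at three linked steps. The p<0.1 screen is run on the cut variable, the model uses the cut variable, and the model's findings choose further subgroups. A true factor that fails the screen cannot reach the later steps. The list of factors also depends on where the cuts fall. BMI shows that a cut is a choice: the superseded subgroup plan split at 28 kg/m² and the current table splits at 24. That difference is not an error, but it shows that no single convention fixes the value.

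**Working it through.** **Inputs.** Event rates of 59.3% (free drainage) and 44.7% (ICCAUT), and 180 evaluable patients per group, come from protocol 11.1 and SAP section 5. The plan gives no figure for information loss and no covariate distributions, so distributions and effect sizes below are assumptions, shown as ranges.

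**Step 1: the plan's own figure.** With unpooled variances, two-sided α = 0.05 and 80% power:

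n = (1.960 + 0.842)² × (0.447×0.553 + 0.593×0.407) / (0.593 − 0.447)² = 7.849 × 0.4885 / 0.02132 ≈ 179.9, so 180 per group and N = 360. (SAP section 5 says one-sided, which gives about 142. That is a separate matter.)

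**Step 2: information lost by a two-level cut.** For a normal covariate with a linear effect, cut at c with upper share p, the loss is 1 − φ(c)² / [p(1−p)].

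- 50/50: 1 − 0.3989²/0.25 = 1 − 0.637 = 36%
- 65/35: 1 − 0.3704²/0.2275 = 1 − 0.603 = 40%
- 80/20: 1 − 0.2800²/0.16 = 1 − 0.490 = 51%

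For a uniform covariate the loss is 1 − 3p(1−p): 25% at 50/50 and 28% at 60/40. For one skewed (lognormal) case it is 63% at 50/50 and 44% with 20% above the cut. The normal case is therefore neither the best nor the worst.

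**Step 3: three-level scores (IPSS, ICIQ-SF).** For a standardised normal covariate the loss is 1 − Σ P_k m_k², where P_k is the share and m_k the mean in class k.

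- near-equal classes: 19–21%
- 50/30/20: 24%
- 60/30/10: 30%
- 70/25/5: 38%
- 80/15/5: 48%

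**Step 4: power to detect the risk factor.** Logistic model with treatment and one normal covariate, N = 360, the plan's event rates, 3,000 simulated trials per scenario, p<0.05:

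| OR per SD | Kept continuous | Cut in two | Splits covered |
|---|---|---|---|
| 1.25 | about 54% | 36–40% | 50/50, 65/35 |
| 1.35 | about 78% | 60%, 56%, 46% | 50/50, 65/35, 80/20 |
| 1.5 | 96% | 83–84% | 50/50, 65/35 |
| 2.0 | about 100% | about 100% | 50/50, 65/35 |

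At an OR of 1.35, the chance of passing the p<0.1 screen is 86–87% kept continuous, against 72%, 68% and 59% for the three splits.

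**Step 5: the adjusted treatment effect, same simulations (50/50 and 65/35).**

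| Covariate OR per SD | Treatment power, continuous | Treatment power, cut in two |
|---|---|---|
| 1.25 | 79–80% | 79–80% |
| 1.5 | 81–82% | 80–81% |
| 2.0 | 82% | 81% |

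The largest gap in any scenario is 82.3% − 80.5% = 1.8 points. At a covariate OR of 2.0 the mean treatment OR is 0.518 with the covariate continuous and about 0.53 with it cut.

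**The case against.** The best defence is that the cuts are fixed in advance. The table shells give every cut-point, the IPSS and ICIQ-SF bands are set out in the protocol appendices, and the protocol's summary of changes gives a reason for the ICIQ-SF grading. This largely closes off the more serious danger of choosing cuts after seeing the data. High-versus-low odds ratios are also easier for clinicians to read. These points stand, but prespecifying a cut does not restore the information it discards, and neither analysis section explains why the other variables are cut.

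It is also fair to say that the model is supportive and that strong factors are found either way. The simulation confirms this at an OR of 2.0. The loss falls on modest factors.

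The per-protocol set excludes non-adherent patients, so it may hold fewer than 360. Absolute power would then be lower than shown under either approach.

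A reader might infer that the adjusted treatment comparison is weakened too. Randomisation makes treatment roughly independent of these covariates, and step 5 shows almost no effect. Per-protocol exclusions happen after randomisation, so some imbalance within age bands is possible, but the documents do not allow it to be sized.

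**Conclusion.** The point holds for the risk-factor analysis and what follows from it: the p<0.1 screen, the multivariable model and the data-selected subgroups. For a modest factor (OR 1.25 to 1.5 per SD) cut between 50/50 and 65/35, about 12 to 22 points of power are lost; at OR 1.35 with an 80/20 split the loss is about 32 points (78% − 46%). These figures assume a normal covariate with a linear effect and 360 patients.

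Two wider readings are not supported. First, the primary result is not in question, because the ITT risk difference uses no covariate. Second, it cannot be said that every cut discards a third or more of the information. That holds for a two-level cut of a roughly normal covariate, but a uniform covariate loses about 25% at the median and the three-level scores can lose about 20%. The actual loss in this trial is unknown until the distributions are seen.

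This is a worthwhile improvement to a secondary analysis and does not threaten the main conclusion.

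**What to change.** 1. Delete the categorisation sentence in SAP 6.5.1 and protocol 11.4.1.
2. In the adjustment list of both documents and in the SAP multivariable table, replace age cut at 65 with age as a continuous term, linear or as a 3-knot restricted cubic spline.
3. Screen BMI, tumour distance, operation time, urine output, infusion volume, IPSS and ICIQ-SF as continuous variables by univariable logistic regression. Chi-square and Fisher's tests cannot take a continuous variable, so deleting the sentence alone would not be enough.
4. Carry those that meet the existing p<0.1 rule into the model as continuous terms. This does not force all seven in.
5. Keep the cut-points for descriptive tables and the prespecified age subgroup.

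The cost is an amendment to both documents and revised table shells. No new data are needed, because SAP 6.4 already records these variables as continuous. Odds ratios would be reported per unit, for example per 10 years, instead of high versus low. The SAP states that it was written before enrolment was complete; the change should be made before the analysis begins.

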6.5.2.1 Sensitivity analysis of missing data

If the missing rate of the primary endpoint is < 5%, no imputation of the primary

endpoint will be done in the ITT analysis set. If the missing rate of the final primary endpoint is $\geq 5\%$, data imputation will be carried out according to the imputation scheme for missing primary endpoint data in Figure 1 in the ITT analysis set.

For the sensitivity analysis in both of the above situations, all missing primary endpoints will be imputed as positive events or all as negative events. Then, the analysis of these two extreme cases will be performed in the ITT population.

6.5.2.2 Sensitivity analysis for positive primary endpoints caused by reasons other than urinary retention

In this study, some patients may have secondary catheterization for reasons other than urinary retention. These events can include:

- 1) Patients ask for secondary catheterization because of urgent urination or a strong fullness feeling, but the urine volume drained after secondary catheterization is no more than 100 ml.
- 2) Patients need secondary catheterization due to situations like unplanned secondary surgery, urethral injury, shock, consciousness disorder, intestinal obstruction, bleeding, transfer to ICU, etc.

In such cases, we still record it as a positive primary endpoint, but will conduct a sensitivity analysis for these cases.

For these patients:

1. If there is data on the bladder residual urine volume after the first urination and it is > 100 ml, it is still regarded as a positive primary endpoint, and no sensitivity analysis is done.
2. If there is no data on the bladder residual urine volume after the first urination or it is ≤ 100 ml, then a sensitivity analysis is needed. In the sensitivity analysis, these patients will be treated as negative events for the primary endpoint.

Sensitivity analysis of primary endpoint:

Dataset: ITT

Variables	Free-drainage group N=***	ICCAUT group N=***	Absolute risk difference (95% CI)	P value
Urinary dysfunction: all missing primary endpoints are imputed as positive events	** (**)	** (**)	** (** to **)	*.***
Urinary dysfunction: all missing primary endpoints are imputed as negative events	** (**)	** (**)	** (** to **)	*.***
Urinary dysfunction: Cases resulting from reasons other than urinary retention are defined as negative primary endpoints, and all missing primary endpoints are imputed as positive events	** (**)	** (**)	** (** to **)	*.***
Urinary dysfunction: Cases resulting from reasons other than urinary retention are defined as negative primary endpoints, and all missing primary endpoints are imputed as negative events	** (**)	** (**)	** (** to **)	*.***

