11.4.2.1 Sensitivity Analysis of Missing Data

If the final missing rate of the primary endpoint is less than 5%, no imputation of

the primary endpoint will be carried out in the primary analysis ITT analysis set. If the final missing rate of the primary endpoint is $\geq 5\%$, data imputation will be performed according to the imputation scheme for missing data of the primary endpoint shown in Figure 2 within the primary analysis ITT analysis set. In the sensitivity analysis, for both of the above - mentioned situations, we will impute all missing data as either positive events or negative events, and conduct analyses for these two extreme scenarios in the ITT population.

11.4.2.2 Sensitivity Analysis of Positive Primary Endpoint Events Caused by Non - urinary Retention Reasons

In this study, some patients may undergo secondary catheterization due to reasons other than urinary retention. Such events may include the following situations:

1) The patient strongly requests secondary catheterization due to urgent urination or a strong sense of fullness, but the volume of urine drained after secondary catheterization does not exceed 100 ml; 2) The patient needs secondary catheterization due to disease - related factors (such as secondary surgery, urethral injury, shock, disturbance of consciousness, intestinal obstruction, bleeding, transfer to the ICU, SOFA score ≥ 2 , etc.). In such cases, we still record them as positive primary endpoint events, but sensitivity analyses will be conducted for these cases.

For these patients, if 1) there is data on the post - void residual urine volume after the first urination, and the post - void residual urine volume after the first urination is > 100 ml, the primary endpoint is still considered positive, and no sensitivity analysis will be performed. If 2) there is no data on the post - void residual urine volume after the first urination, or the post - void residual urine volume after the first urination is ≤ 100 ml, a sensitivity analysis is required. In the sensitivity analysis, these patients will be treated as negative events of the primary endpoint.

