11.4.2 Sensitivity Analysis of the Primary Endpoint		add section "11.4.2 Sensitivity Analysis of the Primary Endpoint"	Since there may be missing values for the primary endpoint or positive primary endpoint events caused by non-urinary retention reasons, sensitivity analyses are added to ensure the robustness of the analysis results.
11.4.3 Analysis of secondary endpoints	We will consider using sensitivity analysis to explain the impact of missing data on overall results.	Missing values of the secondary endpoints will not be imputed, nor will sensitivity analyses be conducted for them.	The secondary endpoints are not the main research objectives. It is clearly stated that no imputation or sensitivity analysis will be conducted for them.
11.4.4 Subgroup analysis	We will explore differences in the rate of secondary catheterization between the two groups in different subgroups through subgroup analysis. Subgroups include Sex (male; female), age (≤ 65 years; >65 years), ASA classification ($\leq II$; $> III$), BMI (≥ 28 kg/m 2 ; <28 kg/m 2), the relationship between the lower edge of the tumor and the peritoneal reflection (above the peritoneal reflection; below the peritoneal reflection), Operating time (≤ 180 mins; >180 mins), neoadjuvant therapy (Yes, No), and surgical procedures (LAR surgery; APR surgery; TaTME surgery; Bacon surgery; ISR surgery; CAA surgery).	We will explore the differences in the primary endpoints between the two groups in different subgroups through subgroup analysis. The subgroups include gender (male; female), age (≤ 65 years old; > 65 years old), the relationship between the lower part of the tumor and the peritoneal reflection (above the peritoneal reflection, below the peritoneal reflection), as well as other variables that are independently related to the primary endpoint in the multivariate analysis.	The objectives of the subgroup analysis, the criteria for subgroup classification, and which variables are eligible for subgroup analysis have been redefined. This is to avoid conducting subgroup analysis on unnecessary variables.
11.5 Exploratory Analysis		add section "11.5 Exploratory Analysis"	The new protocol clarifies the target objects and analysis methods of the exploratory analysis.
11.7 Final analysis		Add the content: "The results of the exploratory analysis will be published separately as a post-hoc analysis."	The reporting time for the exploratory analysis has been supplemented.

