4.2 Secondary endpoints

The secondary endpoints of this study are as follows: 1) the incidence of urinary tract infections associated with the catheter, 2) the time to first void after catheter removal, 3) CRBD grade, 4) evaluation of voiding function after catheter removal using the ICIQ-SF and International Prostate Symptom Score (IPSS), 5) Evaluation of the incidence, type, and grade of complications within 30 days postoperatively, and 6) Incidence rate of residual urine volume greater than 200 ml after the first voiding.

5 Sample size

The sample size is calculated based on a differential test, with urinary dysfunction as the primary endpoint. Based on our preliminary research results, the incidence of urinary dysfunction in the bladder training group is 44.7%, and in the direct removal group, it is 59.3%. Patients are randomly assigned to the two groups in a 1:1 ratio. With a one-sided significance level α of 0.05 and a power (1- β) of 80%, the sample size was calculated using PASS 15 software. Each group, the bladder training group and the direct removal group, requires 180 cases. Assuming a dropout rate of 10%, each group requires 200 cases. Therefore, this trial needs a total of 400 cases.

6 Statistical methods

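### The two planned extreme cases for missing primary endpoints give both arms the same outcome, so they do not bound the risk difference

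*SAP*

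**What the plan says.** SAP 6.5.2.1 sets the sensitivity analysis for missing primary endpoints: "all missing primary endpoints will be imputed as positive events or all as negative events". It then states that "the analysis of these two extreme cases will be performed in the ITT population". Protocol version 2.0, section 11.4.2.1, has the same rule: "we will impute all missing data as either positive events or negative events".

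The SAP's table shell has four rows, each with one column per arm, a risk difference with 95% CI, and a p-value. The first two rows are "Urinary dysfunction: all missing primary endpoints are imputed as positive events" and "Urinary dysfunction: all missing primary endpoints are imputed as negative events". The other two repeat that pair after recoding catheterizations not due to retention; the last reads "Cases resulting from reasons other than urinary retention are defined as negative primary endpoints, and all missing primary endpoints are imputed as negative events". In every row, one outcome applies to missing patients in both arms. Neither document has a row with opposite outcomes by arm, or a tipping-point analysis.

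The effect measure is the absolute risk difference (SAP 6.5.1). The protocol's table of changes to version 2.0 gives the purpose of section 11.4.2: "sensitivity analyses are added to ensure the robustness of the analysis results".

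**The concern.** Giving every missing patient the same outcome moves both arms' event rates in the same direction, so most of the movement cancels in the risk difference. The cases that push the difference furthest give missing patients an event in one arm and no event in the other, and neither is planned.

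These rows are the only planned stress test for missing primary endpoints. If loss is similar in the two arms, the report will show two nearly identical rows presented as extremes. A reader would infer robustness that was not tested.

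Missing outcomes that relate to arm are conceivable here. Patients and nurses know the allocation (protocol 5.2). Refusal and an ultrasound not done in time are both listed as causes of a missing endpoint (SAP 6.3.1).

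**Working it through.** **Inputs.** Design event rates are 44.7% (ICCAUT) and 59.3% (free drainage), with 200 per arm (SAP section 5: "Assuming a dropout rate of 10%, each group requires 200 cases"). The documents give no missing counts, so mI and mF are assumptions.

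**The plan's own figure.** With two-sided α = 0.05 and 80% power, the unpooled formula gives (1.960 + 0.842)² × (0.447×0.553 + 0.593×0.407) / 0.146² ≈ 180 per arm, and 180/0.90 = 200. The design inputs therefore reproduce. (SAP section 5 calls α one-sided, which would give 142; that is a separate point.) The plan states no width for the sensitivity range.

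**Algebra.** Let eI and eF be the observed events, and let x (0 to mI) and y (0 to mF) be the events imputed to missing patients. With n per arm:

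RD = (eI + x)/n − (eF + y)/n

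- All positive: x = mI, y = mF. All negative: x = y = 0. These differ by |mI − mF|/n.
- Largest RD: x = mI, y = 0. Smallest RD: x = 0, y = mF. These differ by (mI + mF)/n.

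The two widths agree only if one arm has no missing endpoints. For unequal arm sizes, use mI/nI and mF/nF.

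**Numbers.** Observed events are the design rate times the number observed, rounded. RD is ICCAUT minus free drainage, in percentage points. CIs are Wald; p-values are from the uncorrected chi-square test.

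| Missing (ICCAUT v FD) | Observed events | All positive | All negative | Allowed range |
|---|---|---|---|---|
| 5 v 5 | 87/195 v 116/195 | −14.5 | −14.5 | −17.0 to −12.0 |
| 9 v 9 | 85/191 v 113/191 | −14.0 | −14.0 | −18.5 to −9.5 |
| 20 v 20 | 80/180 v 107/180 | −13.5 | −13.5 | −23.5 to −3.5 |
| 13 v 5 | 84/187 v 116/195 | −12.0 | −16.0 | −18.5 to −9.5 |
| 18 v 0 | 81/182 v 119/200 | −10.0 | −19.0 | −19.0 to −10.0 |

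Worked example, 20 v 20:
- All positive: 100/200 v 127/200 = −13.5 (p = 0.006).
- All negative: 80/200 v 107/200 = −13.5 (p = 0.007).
- Adverse crossed case: 100/200 v 107/200 = −3.5 (95% CI −13.3 to 6.3, p = 0.48).
- Favourable crossed case: 80/200 v 127/200 = −23.5.

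At the adverse end for the other balanced cases:
- 5 v 5: 92/200 v 116/200 = −12.0 (95% CI −21.7 to −2.3, p = 0.016).
- 9 v 9: 94/200 v 113/200 = −9.5 (95% CI −19.2 to 0.2, p = 0.057). Both planned rows have p = 0.005.

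At 9 v 9 the complete-case estimate is 85/191 − 113/191 = −14.7, so the planned pair does not even bracket the unimputed result.

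**How much of the grid loses p < 0.05.** Testing every (x, y):
- 9 v 9: 1 of 10 × 10 = 100 combinations, namely x = 9, y = 0.
- 20 v 20: every combination with x − y ≥ 8, which is 13 + 12 + … + 1 = 91 of 21 × 21 = 441. For example, x = 14, y = 6 gives 94 v 113 = −9.5, p = 0.057.

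Under balanced loss both planned rows sit at x − y = 0.

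**The case against.** The algebra is not in dispute; the case on the other side concerns size.

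- **The 10% is a dropout allowance, not a forecast of missing endpoints.** It was carried over from a protocol version that removed patients meeting withdrawal criteria from analysis. Version 2.0 deleted those criteria. A patient with either component positive is never missing, and second-void ultrasound, out-of-hours cover and compensation were added. This stands: 20 v 20 is an assumption at the pessimistic end.
- **Below 5% missing, little changes.** This also stands, as the 5 v 5 and 9 v 9 results show.
- **The grid cells are not equally likely.** At 20 v 20, the probability that x − y ≥ 8 is 0.0004 if missing patients follow the design rates, 0.008 if both arms have 52%, and 0.07 if the two design rates are swapped. It is 0.58 at 70% v 30%. Losing significance therefore needs a strong reversal among missing patients. This stands, and it is a reason to show the grid.
- **At 5% or more missing, the primary analysis already imputes by component (SAP 6.3.2).** True, but multiple imputation with substitution of the second-void value does not test outcomes that depend on arm among the missing.
- **The crossed counts can be read from the planned rows.** True of the counts. Their risk difference, CI and p-value are still not prespecified.
- **The label describes the imputed value, not the risk difference.** That reading is possible, but the rows report a risk difference and were added to show robustness.

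**Conclusion.** The concern holds. The planned pair spans |mI − mF|/n of an attainable range of (mI + mF)/n, and collapses to one value when loss is balanced. That result needs no assumption beyond equal arm sizes.

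The practical size depends on missing counts the documents do not give. At the design rates it is small below 5% missing. Near 10%, the planned rows would show −13.5 twice while the data allow anything from −23.5 to −3.5. If all loss falls in one arm, as in 18 v 0, the planned rows already reach the true extremes. The primary analysis is not affected. This is an inexpensive improvement that should be made, not a flaw that undermines the trial.

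**What to change.** In SAP 6.5.2.1 and protocol 11.4.2.1, add two crossed rows: missing ICCAUT patients as events with missing free-drainage patients as non-events, and the reverse. Give each a risk difference, 95% CI and p-value. A tipping-point grid over imputed events by arm would serve instead, and is easier to interpret because it shows how far from balance the conclusion changes. Keep the two planned rows, but describe them as same-direction scenarios.

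The cost is two table rows or one grid, and a sentence in each document. No new data are needed, since the primary-endpoint table in SAP 6.5.1 already reports missing counts by arm. The downside is that the crossed cases are deliberately pessimistic, so robustness may look less favourable; the text should say so.
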